Title:

The effect of audiovisual aids on perioperative stress response, pain and overall experience – a randomized controlled pilot study (AVA Pilot)

NCT# 02506673

Date: 9/18/19

Title:

The effect of audiovisual aids on perioperative stress response, pain and overall experience – a randomized controlled pilot study (AVA Pilot)

What is the condition or intervention to be studied?

The effect of personal audiovisual equipment (audio/video goggles) on perioperative stress, pain and overall experience in patients undergoing ambulatory meniscectomy under spinal anesthesia.

What is/are the research question(s)/specific aim(s)?

- 1) Evaluate the feasibility of the use of personal audiovisual equipment in patients undergoing meniscectomies under spinal anesthesia
- 2) Determine outcome estimates of the use of this equipment on stress levels using skin conductance measurement methodology, request for further sedation, postoperative pain levels and analgesic consumption, time to discharge readiness, and overall patient satisfaction
- 3) Collect thus far unavailable data on the stress response to perioperative stresses (such as IV insertion and spinal placement) in order to allow for power analyses for future studies

What is/are the hypothesis(es)?

- 1) The perioperative use of personal audio visual aids is feasible in the ambulatory surgical arena for meniscectomies under spinal anesthesia
- 2) The use of the audiovisual aid leads to a reduction in perioperative stress, less need for sedatives, lower postoperative pain levels and increased patient satisfaction comparable or superior to a more traditional sedation approach.

Primary outcome will be number of skin conductance responses per second (SCR/sec) and amplitude of skin conductance responses averaged over time in 5 minute intervals and at key time points such before, during and after insertion of an IV, discussion with surgeon, anesthesiologist, immediately before leaving the holding area, immediately after entering the OR, during application of monitors, before and after administration of sedatives, before, during and after spinal insertion, incision, immediately prior to leaving the OR, after arrival at PACU and monitors are placed, before discharge.

Identify and define the secondary outcome(s) and when they will be measured

- Heart rate, blood pressure and respiratory rate absolute and percent change
- Number of requests of additional sedation

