**Certain time points will be flagged in the recordings: before, during and after insertion of an IV, discussion with surgeon, anesthesiologist, leaving holding area, entering OR, application of monitors, administration of sedatives, before, during and after spinal insertion, incision, leaving OR, entry to PACU, resolution of spinal*

NOTE: After conducting the interim analysis and plotting the skin conductance data, we have determined that the graphs are not consistent enough to draw any conclusions. Given the technical difficulties we have encountered with the MedStorm Stress Detector, as well as the labor intensity associated with it, we have decided that we will no longer use it from patient 14 on. We will not mark hand movements, as this data was used to understand the skin conductance data. We will continue to enroll patients to complete this pilot/exploratory study, as the other secondary outcomes in particular, the surveys could provide valuable information. Patient satisfaction questionnaires will be the priority in our data analysis the "new primary outcome."

When the data will be collected?

Data will be collected on the day of surgery in the holding area, during the procedure, in the PACU until discharge, and on post-operative day 1

The following source will be used:

- Medical Records
- Patient
- No Private Office Charts Please specify which private office:
- No Registries

Sample Size and Data Analysis

Patients will be randomly assigned to one of two groups each composed of 15 patients. A computer generated randomization table will be generated by a statistician. A concealed allocation randomization schema will be used with randomization to occur after the patient consents to be in the research study. This is an un-blinded study group assignment is not concealed from the patients and the treating physicians.

1. Audiovisual equipment (Zeiss Cinema ProMED; HappyMed System) in the holding area OR and PACU + 2 mg Midazolam upon arrival in OR
2. Traditional sedation with 2 mg midazolam upon arrival in OR (control)

Phone follow ups, survey administrations and the use of the audiovisual device are not standard of care. The Department of Anesthesiology Research and Education Fund will cover the associated costs.

Instruments and questionnaires to be used on this study:

- CSQ 8
- State-Trait Anxiety Inventory

Describe any risks to participants in the Placebo or No-Treatment Arm of the study:

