There are no known risks at this time to participants in the no-treatment arm of the study.

Provide a scientific or ethical justification for using a Placebo or No-Treatment Arm:

This is considered a desirable characteristic of randomized controlled trials. Since the protocols for both groups are otherwise identical, any differences between the groups may be attributed to whether or not patients are using the audio visual aid.

Sample size and data analysis:

Is this is a case series based only on the patients available using descriptive statistics in lieu of a sample size calculation?

Yes

Data Analysis:

We will provide means/medians with SD or IQR as per distribution and differences with 95% CI for all outcomes.

We would like to undertake an interim analysis to assess the overall quality of the skin conductance data collected thus far by the MedStorm Stress Detector. Data will be considered of reasonable quality if there is limited variability in skin conductance values over very small periods of time (i.e., a few seconds or less) in the absence of disruptive stimuli, such as hand movements.

We may also compare the range of values found in our data to those reported in previously published studies that used the MedStorm Stress Detector. This is another way in which we can check the quality of our measurements.

Because this is a pilot study with a relatively small projected sample size, we believe it is important to perform this interim analysis to ensure that the instruments used to collect the skin conductance data a primary outcome for this pilot study are reliable.

Describe how, when, and where the consent process will be initiated:

Patients matching the inclusion criteria for this study will be identified the day before surgery. Patients will be approached about the study in the holding area on the day of surgery. Written consent for all patients will be obtained by research staff or co-investigators.

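### Does the plan need amending because skin conductance was abandoned after patient 13 but is still worded as the primary outcome?

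*Combined protocol and SAP*

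**What the plan says.** The outcome paragraph after the hypotheses reads "Primary outcome will be number of skin conductance responses per second (SCR/sec) and amplitude of skin conductance responses", to be "averaged over time in 5 minute intervals and at key time points" through the perioperative course. Specific aim 2 includes "Determine outcome estimates of the use of this equipment on stress levels using skin conductance measurement methodology". Specific aim 3 seeks data on responses to perioperative stresses "in order to allow for power analyses for future studies"; it gives IV insertion and spinal placement as examples and names no instrument. The secondary outcomes include "Heart rate, blood pressure and respiratory rate absolute and percent change".

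Data Analysis promises location and spread for every outcome, with "differences with 95% CI for all outcomes". It then proposes an interim check of recording quality, justified by the need to be sure of the instruments behind "the skin conductance data a primary outcome for this pilot study".

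The NOTE below the list of flagged time points reports the result of that check: "the graphs are not consistent enough to draw any conclusions". It cites technical difficulties and workload, ends use of the detector from patient 14, drops the marking of hand movements, continues enrolment for the other outcomes, and makes the satisfaction questionnaires the new primary outcome.

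**The concern.** Three things look wrong at first. The outcome paragraph and aim 2 were not revised after the NOTE, so the document names two different primary outcomes. The reporting rule in Data Analysis has no exception, so taken literally it requires arm differences and intervals for recordings the team considers unfit for conclusions. And no sentence says whether the recordings from patients 1 to 13 are to be analysed, listed or left out.

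If this mattered, an unqualified interval on an unreliable measure could be read as evidence about the device, or its standard deviation could be carried into the planning of a later trial under aim 3. A reader who saw only the outcome paragraph would also miss that the primary outcome was replaced after an interim look. A further doubt is that heart rate, blood pressure and respiratory rate are listed under the detector's heading, so stopping the detector might seem to stop them too.

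**Working it through.** **Inputs.** Planned enrolment is 30, in two groups of 15 (Target Enrollment; Sample Size and Data Analysis): 2 × 15 = 30. The detector stops from patient 14 (NOTE). The plan gives no power calculation, standard deviation or precision target; it answers yes to descriptive statistics in place of a sample size calculation.

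**How many patients are affected.** At most 14 − 1 = 13 patients can have recordings: 13/30 = 43.3%. If all 30 are enrolled, at least 30 − 13 = 17 have none: 17/30 = 56.7%. The number of usable recordings among the 13 is not stated.

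**What an interval would look like.** For a difference in means, the 95% half-width in SD units is t(0.975, n1+n2−2) × √(1/n1 + 1/n2). The arm split of the first 13 is not given, so the two splits below are assumptions.

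| Split | t | √(1/n1 + 1/n2) | Half-width |
|---|---|---|---|
| 15/15 (planned) | 2.048 | 0.365 | 0.75 SD |
| 6/7 | 2.201 | 0.556 | 1.22 SD |
| 4/9 | 2.201 | 0.601 | 1.32 SD |

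Intervals this wide show that the data are weak, but no precision target exists for them to miss. They reflect sampling error only. The measurement failure cannot be sized, because the documents give no reliability figure.

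**How many differences the rule would generate.** The plainest reading of the listed events gives 17 time points: IV 3, surgeon 1, anesthesiologist 1, leaving holding 1, entering OR 1, monitors 1, sedatives 2, spinal 3, incision 1, leaving OR 1, PACU 1, discharge 1. With two measures that is 34. If the before-during-after wording also covers the two discussions, it is 17 + 4 = 21 time points, or 42 differences. The list is illustrative, so neither count is firm.

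**Which text governs.** The phrase calling skin conductance a primary outcome in Data Analysis belongs to the argument for doing the interim check, written as a proposal. The NOTE reports that check as done and acts on it, so the two are successive stages and not rival statements. Only the outcome paragraph and part of aim 2 are plainly out of date. A general reporting sentence does not override a specific statement that no conclusions can be drawn from one measure.

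**Aim 3 and the vital signs.** Aim 3 does not name skin conductance, and nothing in the plan proposes using its standard deviation for planning. The detector heading also covers complications, which no skin sensor records, so it is not a clean list of device outputs. Standard ASA monitoring is specified for all patients and medical records are a listed source. The NOTE ends the detector and the hand-movement marking, and says the other secondary outcomes remain of interest.

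**The case for a change.** The strongest case for a change is that the NOTE is live plan text and the rest of the document was not brought into line with it. The quality criterion states no consequence for data that fail it. Two careful analysts could therefore differ: one would tabulate differences with intervals for the first 13 patients, and the other would report nothing. The background stresses the lack of skin conductance data, so a reader might well treat these recordings as what aim 3 was meant to deliver. An amendment would cost only wording.

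Much of the description stands: the outcome paragraph is out of date, the handling of the recordings is unstated, and the NOTE is silent on whether events are still flagged after patient 13, although flags were placed in the recordings. The consequence does not follow. Either analyst would be working under a statement that these data support no conclusions, so the choice changes no finding the study relies on. Exempting the original primary outcome from the interval rule is not clearly better. Showing the results with n per arm and a caveat is equally defensible and less open to a charge of selective reporting. Confining aim 3 to the remaining measures gains little: the anxiety inventory is taken after consent and before discharge, and at neither of aim 3's example events.

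**Conclusion.** The concern describes the text accurately but does not call for a change. The NOTE already does the substantive work: it declares the recordings unfit for conclusions, fixes the stopping point, gives reasons and names the replacement outcome. The missing reporting sentence is a gap an analyst would fill sensibly, by keeping skin conductance visible as the original primary outcome, stopped after the interim look, and attaching n per arm, the reason for stopping and a reliability caveat to any summary.

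The firm size is at most 13 of 30 patients (43%) with recordings. The half-widths rest on assumed arm splits, and the counts of 34 or 42 differences on how one list is read; neither supports a finding. The conclusion assumes that the NOTE is read as superseding the earlier outcome wording and that vital signs continue under routine monitoring. The documents support both readings, though they do not state the second outright. The outdated outcome wording and the event-flag question are minor editorial matters.

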- NRS levels in PACU until discharge and day after surgery

- narcotic consumption in PACU and cumulative over 24 h after PACU discharge pre (after consent) and postoperative (before discharge) anxiety level (State Trait Anxiety Inventory)
- patient satisfaction (Heidelberg Peri-Anaesthetic Questionnaire) in PACU upon spinal resolution
- patient feedback (CSQ8) in PACU upon spinal resolution provider feedback (form sent to providers at end of surgery day)
- Request for sedation/termination of AVA
- complications (headache, transient neurologic symptoms, nausea and vomiting, ...)

Explain why these research questions are being asked:

Little is known about perioperative stress responses and possible anxiety mitigating factors like audiovisual aids or even. IV sedation. Most studies use surrogate markers and retrospective questionnaires, not based on real time gathered data. With skin conductance measurements the sympathetic discharge can be evaluated down to fractions of a second and enables us therefore to continuously monitor stress responses as skin conductance responses/per second during the perioperative management.

What is the background of the topic that you believe is important for the reviewer to know in considering this protocol, including prior studies by this research team. Describe strengths and deficiencies of prior studies; explain how this study fits in. Include references.

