Patients matching the inclusion criteria for this study will be identified the day before surgery. Patients will be approached about the study in the holding area on the day of surgery. Written consent for all patients will be obtained by research staff or co-investigators.

Please select enrollment type from following drop down list:

Over Course of Study

Target Enrollment

What is the maximum number of subject you plan to enroll in this study?

30

How subjects will be identified

- Potential subjects will be identified after a review of medical records of patients under the care of one or more of the study investigators
- Medical records and/or other Institution sources (databases, registries, billing records, pathology reports, and admission logs) will be reviewed to identify potential participants. May involve access of records by individuals not involved in the patient's care.

We will enroll patients scheduled for primary, ambulatory, arthroscopic meniscectomy under spinal anesthesia, as complete surgical anesthesia can be provided to the surgical site and sedation is essentially optional.

After obtaining written informed consent in the holding area, the research staff will attach a skin conductance device to the patients to measure levels of sympathetic discharge (MedStorm Stress Detector). We will administer the State Trait Anxiety Inventory (STAI) immediately after obtaining consent in the holding area and in the PACU before discharge.

Patients will be randomly assigned to one of two groups, each composed of 15 patients:

1. Audiovisual equipment (Zeiss, Cinema ProMED; HappyMed System) in the holding area, OR and PACU + 2 mg midazolam upon arrival in OR
(Patients can choose audiovisual content from a preexisting library of nature programs)
2. Traditional sedation with 2 mg midazolam upon arrival in OR

Patients can change their mind anytime and ask for additional sedatives in 1 mg increments of midazolam. The spinal anesthetic administered will be up to 3.5 cc 1.5% mepivacaine or between 23 cc 2% chloroprocaine at the discretion of the anesthesiologist. There will be standard ASA monitoring with O2 administered via nasal cannula. 4 mg ondansetron and up to 30 mg ketorolac will be administered as per routine. Hemodynamic instability will be treated as per clinical judgment of the attending

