anesthesiologist with ephedrine, beta blockers or other medications as indicated. Because intraoperative administration of ketorolac, dexamethasone, and periarticular prednisone and morphine could affect pain management, we will record information (dose, amount) about these medications.

Equipment will be removed in the PACU at the patient's request or upon spinal resolution. After spinal resolution, patients will complete the Heidelberg Perianaesthetic Questionnaire. If patients are randomized to the audiovisual equipment group, they will also provide feedback regarding their experience with the audiovisual equipment when they complete the CSQ8 questionnaire. Providers will also receive a survey about the audiovisual equipment at the end of the surgery day.

On POD 1, patients will report their opioid consumption and pain level since discharge.

Data will be collected:

Day of Surgery Preoperatively: from chart and patient interview

- a. Patient demographics – date of birth, race, ethnicity, gender, education level, prior surgeries
- b. State-Trait Anxiety Inventory (STAI) score
- c. NRS pain scores at rest
- d. Start time of Zeiss and HappyMed System audiovisual aids

PACU: from chart and patient interview.

- a. Anxiolytic, hemodynamic and opioid medication consumption (Also recording intraop administration of ketorolac, dexamethasone, and periarticular prednisone and morphine)
- b. End time of Zeiss and HappyMed system audiovisual aids (start and end times will be used to calculate total viewing time)
- c. Type of movie/program viewed on Zeiss and HappyMed System audiovisual aids
- d. NRS pain scores at rest
- e. STAI score
- f. Patient satisfaction (Heidelberg Perianaesthetic Questionnaire score)
- g. Patient feedback regarding use of audiovisual equipment (if randomized to that group)
- h. Provider feedback regarding use of audiovisual equipment (survey sent via email at end of surgery day)

Continuous Throughout Hospital Stay*: MedStorm Stress Detector

- a. Skin Conductance responses per second
- b. Amplitude of skin conductance responses
- c. Heart rate
- d. Blood pressure
- e. Respiratory rate
- f. Complications

Postoperative Day 1: patient interview

- a. NRS pain scores at rest
- b. Opioid medication consumption

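### Adjusting post-operative STAI for the pre-operative score is an optional, nearly free precision gain that the plan leaves unused

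*Combined protocol and SAP*

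**What the plan says.** The list of secondary outcomes includes "pre (after consent) and postoperative (before discharge) anxiety level (State Trait Anxiety Inventory"). The study procedures place the two administrations "immediately after obtaining consent in the holding area and in the PACU before discharge". The data-collection list names the pre-operative item only as "State-Trait Anxiety Inventory (STAI) score", and the PACU item is no more specific, so neither says which scale is meant.

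The whole analysis rule, under Data Analysis, is "We will provide means/medians with SD or IQR as per distribution and differences with 95% CI for all outcomes". No model or covariate is named anywhere. For heart rate, blood pressure and respiratory rate, the secondary-outcome list asks for values and for percentage change. It asks for no change measure for STAI.

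Under Sample Size and Data Analysis there are two arms of 15, with "randomization to occur after the patient consents to be in the research study" and with the statement that "group assignment is not concealed from the patients and the treating physicians". The intervention arm receives "Audiovisual equipment (Zeiss, Cinema ProMED; HappyMed System) in the holding area, OR and PACU".

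The note after the interim analysis drops skin conductance from patient 14 on. It continues enrolment because "the surveys could provide valuable information" and gives priority to the satisfaction questionnaires.

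**The concern.** Each patient supplies an anxiety score on the same instrument before and after surgery. If the two scores are correlated, part of the spread in the post-operative scores is predictable from the first one, and a comparison that ignores it carries that spread into the confidence interval. In a 30-patient pilot whose output is estimates with intervals, this is information already collected and not used.

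What is at stake is the width of one secondary interval, and how well it allows for whatever chance baseline difference the randomization happens to produce. Validity is not at stake. The pre-operative score serves as a baseline only if the patient completes it before learning the arm. That is why the order of STAI and allocation belongs to the same point.

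**Working it through.** The plan gives no STAI standard deviation, correlation or target precision, so it has no figure to reproduce.

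**Inputs.** From the documents: 15 per arm (N = 30) and 95% intervals. Assumed: r from 0 to 0.7, normal scores, and both scores available from every patient. Widths are in units of the within-arm SD of the post-operative score. The t quantiles are 2.0484 (28 df) and 2.0518 (27 df).

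**Unadjusted half-width.** t28 × √(2/15) = 2.0484 × 0.3651 = 0.748 SD.

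**Adjusted half-width, on average.** t27 × √[(2/15)(1 − r²)(27/26)]. The factor 27/26 = 1 + 1/(N − 4) is the average cost of chance baseline imbalance, and moving from 28 to 27 df is the cost of the extra term. At r = 0.5: 2.0518 × √(0.1333 × 0.75 × 1.0385) = 2.0518 × 0.3222 = 0.661 SD, and 0.661/0.748 = 0.884.

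The last two columns come from a simulation of 400,000 bivariate-normal trials per r, with equal SDs and no treatment effect.

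| r | Adjusted half-width (SD) | Adjusted/unadjusted | Trials where adjusted CI is wider | Mean ratio when arms differ at baseline by > 0.5 SD |
|---|---|---|---|---|
| 0 | 0.763 | 1.021 | 80% | 1.066 |
| 0.2 | 0.748 | 1.000 | 60% | 1.045 |
| 0.3 | 0.728 | 0.974 | 40% | 1.017 |
| 0.5 | 0.661 | 0.884 | 9% | 0.924 |
| 0.7 | 0.545 | 0.729 | 0.5% | 0.761 |

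**Break-even.** Setting the two widths equal gives r² = 1 − 1/[(27/26)(t27/t28)²] = 1 − 1/1.0419 = 0.0402, so r = 0.201. With fewer patients giving both scores it rises: 0.209 at 14 per arm, 0.219 at 13, 0.230 at 12 and 0.258 at 10.

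**Chance imbalance.** The baseline difference between arms has SD √(2/15) = 0.365, so it exceeds 0.5 SD with probability P(|Z| > 0.5/0.365) = 0.171. In the same simulation, the unadjusted interval covered 0.925, 0.886 and 0.824 in those trials at r = 0.3, 0.5 and 0.7. In the remaining trials it covered 0.955, 0.963 and 0.976. The two groups average out: at r = 0.5, 0.171 × 0.886 + 0.829 × 0.963 = 0.950. Adjusted coverage was about 0.95 in both groups.

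**The case against.** The strongest reply is that nothing here is wrong. The study is declared descriptive, with no sample size calculation. STAI is secondary, no decision rule uses it, and the re-designated priority outcome, satisfaction, has no baseline score to adjust for. The correlation is unknown, and below about 0.2 adjustment gains nothing. All of this stands, and it limits the point to a suggestion.

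A reader might also infer four stronger things that the documents or the arithmetic do not support.

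- **That the unadjusted comparison is biased or under-covers.** It is unbiased under randomization and covers 95% overall. The lower coverage figures apply only to the 17% of trials with a large baseline imbalance, and they are balanced by over-coverage in the rest.
- **That the STAI contrast is undefined.** The plan asks for change where it wants change, for the vital signs. The natural reading for STAI is therefore a difference in level at each time. This is not spelled out, but what is missing is detail.
- **That the pre-operative score is contaminated by knowledge of the arm.** The procedures describe consent, attachment of the sensor and the STAI before they describe assignment. Because the study is open and the device is used in the same holding area, explicit confirmation is worthwhile. The text does not show that the order was reversed.
- **That adjustment narrows the interval whenever r exceeds 0.2.** This holds on average and with complete data. At r = 0.3 the adjusted interval is still wider in about 40% of trials.

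**Conclusion.** The point holds as an optional precision gain on a secondary outcome. The plan collects a usable baseline and its analysis rule does not use it.

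The trade is asymmetric. The average cost is about 2% in width if r is near 0, against a gain of 12% at r = 0.5 and 27% at r = 0.7. The size rests on the assumed r, on normal scores and on both scores being available from all 30 patients. A baseline completed before allocation is revealed is also required. No conclusion of the pilot depends on this choice.

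**What to change.** Before STAI is compared by arm, add to Data Analysis:

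- The between-arm difference in post-operative STAI, with its 95% CI, comes from a linear model with arm and the pre-operative score on the same scale as covariate. Name the scale, for example the state score.
- This adjusted mean difference is reported even if medians and IQRs are used for description, and the unadjusted difference is given alongside.

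In the procedures, add that the pre-operative STAI is completed before allocation is revealed, as the described sequence already suggests.

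The cost is a few sentences, one model term and one degree of freedom, with no new data. The interval would be about 2% wider on average if r is near 0, and about 7% wider if the arms also differ at baseline by more than 0.5 SD.

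### At 15 per arm, one means-or-medians rule for all outcomes can return a zero difference or a zero-width interval for yes/no outcomes and sparse counts; proportions with a score interval avoid this

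*Combined protocol and SAP*

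**What the plan says.** Under Data Analysis, the combined protocol and SAP gives one rule: "We will provide means/medians with SD or IQR as per distribution and differences with 95% CI for all outcomes". It names no count, proportion, risk difference, or exact or score interval, there or elsewhere.

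The secondary outcomes include "Number of requests of additional sedation", a combined item for requesting sedation or terminating the audiovisual aid, and "complications (headache, transient neurologic symptoms, nausea and vomiting", a list left open-ended. Request for further sedation is also named in specific aim 2, and a lower need for sedatives is part of hypothesis 2.

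On size: "Patients will be randomly assigned to one of two groups each composed of 15 patients". The trial is described as using "descriptive statistics in lieu of a sample size calculation".

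In the list of data to be collected, complications have their own item. The nearest item to sedation requests is "Anxiolytic, hemodynamic and opioid medication consumption", which records drug given. The time points flagged in the recordings also refer to giving sedatives, not to requests for them.

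**The concern.** A median carries little information about a yes/no item or a count that is mostly zeros. The instruction to choose by distribution sends a skewed count to the median and IQR. In a small arm, both medians can then be 0 although the arms differ. If the mean is used instead, a trial with no events in either arm has zero sample variance, and the usual interval shrinks to a single point.

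This pilot is meant to produce outcome estimates, with request for sedation among them, so the estimates and intervals are its product. A row reading 0 versus 0, difference 0, would give a later trial little to plan with. An interval of 0 to 0 for complications would look far more precise than 30 patients allow.

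**Working it through.** **Inputs from the documents.** n = 15 per arm; a 95% CI, taken as two-sided because sidedness is not stated. The plan's only size figure reproduces: 2 × 15 = 30, the stated maximum enrollment. There is no power calculation to reproduce.

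**Assumed inputs.** The documents give no event rates. A range is used, with the same rate p in both arms and independent patients.

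**Median branch.** The median of 15 values is the 8th in order. It is 0 if at most 7 patients have a nonzero value. Both medians are 0 with probability [P(Bin(15, p) ≤ 7)]².

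| Assumed p | One arm | Both arms |
|---|---|---|
| 20% | 0.996 | 99.2% |
| 30% | 0.950 | 90.2% |
| 40% | 0.787 | 61.9% |
| 50% | 0.500 | 25.0% |

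If the number of requests is taken as Poisson with mean m, then p = 1 − exp(−m). Both medians are 0 with probability 95.7% at m = 0.3, 64.3% at 0.5, 23.9% at 0.7 and 2.1% at 1.0. The problem fades once more than about half of the patients make a request.

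**Mean branch.** The interval has zero width if neither arm has an event (or if every patient does). The probability of no events is (1 − p)^30: 0.98^30 = 54.5%, 0.95^30 = 21.5%, 0.90^30 = 4.2%. Any mixed result gives an interval with width: 0/15 versus 1/15 is −6.7 points, Wald CI −19.3 to +6.0.

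**Comparison with a score interval.** The Wilson limits for x/n, with p = x/n and z = 1.96, are [p + z²/2n ± z√(p(1−p)/n + z²/4n²)] / (1 + z²/n). Newcombe's interval for d = p₁ − p₂ runs from d − √((p₁−l₁)² + (u₂−p₂)²) to d + √((u₁−p₁)² + (p₂−l₂)²).

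- *0/15 versus 0/15.* Wilson upper limit = 3.84/(15 + 3.84) = 0.204. Newcombe: −20.4 to +20.4 points. Mean-based Wald or t: 0 to 0.
- *3/15 versus 0/15.* Wilson limits are 0.070 to 0.452 and 0 to 0.204. Difference 20 points; Newcombe lower limit 0.200 − √(0.130² + 0.204²) = −0.042, upper limit 0.200 + √(0.252² + 0²) = 0.452. Median branch: both medians 0, both IQRs 0–0, bootstrap CI for the median difference 0 to 0.
- *7/15 versus 1/15.* Wilson limits are 0.248 to 0.699 and 0.012 to 0.298. Difference 40 points; Newcombe lower limit 0.400 − √(0.219² + 0.231²) = 0.082, upper limit 0.400 + √(0.232² + 0.055²) = 0.639. Median branch: difference 0, IQR 0–1 versus 0–0, bootstrap CI 0 to 1.

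**The case against.** The strongest reply is that the rule leaves the choice open. The mean of a 0/1 item is a proportion, so a difference in means with a 95% CI is a risk difference. For 7/15 versus 1/15 the t interval (28 df) is 9.5 to 70.5 points, not far from Newcombe's 8.2 to 63.9. The phrase about all outcomes might also attach only to the differences. This stands in part: for yes/no items the rule is underspecified, not unworkable. For a skewed count, however, the distribution clause points to the median. If the phrase covers only the differences, the yes/no items have no stated summary at all.

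A second reply is that the plan also asks for an IQR and a CI, which partly reveal a large gap. That is true at 7/15 versus 1/15, but not at 3/15 versus 0/15, where every output is 0.

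Two stronger readings are tempting. A reader might infer that the rule will produce wrong results. The documents give no event rates, so only a conditional statement is supported. A reader might also infer that consumption data mix patient requests with clinician-started doses and miss refused requests. The documents describe neither, and extra midazolam appears only as something patients ask for. No case report form is included, so the summary list does not prove that a request field is absent.

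**Conclusion.** The point holds in conditional form. With 15 per arm, the median branch gives a point difference of 0 when each arm has 7 or fewer patients with an event. That is likely if the true rate is at or below about 40%, and much less so from 50% upward. The mean branch gives a zero-width interval only with no events, or all events, in both arms; the former is plausible for rare complications and unlikely from a 10% rate upward. Both statements rest on assumed rates, equal in the two arms.

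That requests will be sparse is a judgement: every patient receives midazolam on arrival in the OR, and the protocol regards sedation as essentially optional for this surgery. The missing request item is a lesser matter of detail, since anxiolytic consumption is a partial proxy and complications are listed.

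The effect is on the reporting of secondary outcomes in a descriptive pilot. The sample size and the satisfaction questionnaires, now the analysis priority, are untouched. The change is still worth making, because the affected outcomes belong to aim 2 and hypothesis 2 and a better method costs almost nothing.

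**What to change.** Amend Data Analysis as follows.

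- **Complications, and any request for additional sedation:** n/N per arm and the risk difference with a score-type 95% CI, for example Newcombe. Another score or exact method would also serve.
- **Termination of the audiovisual aid:** n/N in the audiovisual arm only, with a Wilson or exact 95% CI. The control arm cannot have this event, so no difference is defined.
- **Number of requests:** the distribution and mean count per arm, with a 95% CI for the difference in means and no median. If all counts are zero, any interval for the means, including a bootstrap, also collapses. In that case rely on the score interval for any request.
- **Data list (minor):** add a count of sedation requests.

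The cost is a few lines in the analysis section and one data item. Intervals for rare events will be wider than the mean-based ones, which reflects what 15 patients per arm can show.

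If enrollment is complete and requests were not recorded, report consumption as a proxy and say so.
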